### **6.7.2 Recommended treatment of adverse events**

Medication used to treat adverse events (AEs) must be recorded on the appropriate eCRF. Any treatment deemed necessary by the investigator for the safety of the participant is allowed. For treatment of severe allergic reactions including anaphylaxis, epinephrine and SABA are typically used with or without antihistamines and corticosteroids. Guidance on clinically notable lab values and vital signs ([Section 16.1](#)), monitoring infections ([Section 16.1.1](#)), immunizations ([Section 16.1.2](#)), as well as liver event definitions and follow up requirements ([Section 16.2](#)) and renal alert and actions criteria ([Section 16.3](#)) are provided in appendices ([Section 16](#)).

Treatments of adverse events should align with prohibited medication ([Section 6.2.2](#), [Table 6-4](#)) and medications allowed under certain conditions ([Section 6.2.1.1](#)). Medication used to treat adverse events (AEs) must be recorded on the appropriate eCRF.

Please refer to [Section 16.4](#) for the assessment, reporting and management of hypersensitivity reactions observed during the DBPCFC and the post-DBPCFC observation period.

### **6.7.3 Emergency breaking of assigned treatment code**

Emergency code breaks must only be undertaken when it is required to in order to treat the participant safely. Most often, study treatment discontinuation and knowledge of the possible treatment assignments are sufficient to treat a study participant who presents with an emergency condition. Emergency treatment code breaks are performed using the IRT. When the investigator contacts the system to break a treatment code for a participant, he/she must provide the requested participant identifying information and confirm the necessity to break the treatment code for the participant. The investigator will then receive details of the investigational drug treatment for the specified participant and a fax or email confirming this information. The system will automatically inform Novartis monitor for the site and the study team that the code has been broken.

It is the investigator's responsibility to ensure that there is a dependable procedure in place to allow access to the IRT at any time in case of emergency. The investigator will provide:

- protocol number
- participant number

In addition, oral and written information to the participant must be provided on how to contact the investigator or his/ her backup in cases of emergency, or when he/she is unavailable, to ensure that un-blinding can be performed at any time.

The appropriate personnel from the study site and Novartis will assess whether study treatment should be discontinued for any participant whose treatment code has been broken for any reason.

## **7 Informed consent procedures**

Eligible participants may only be included in the study after providing (witnessed, where required by law or regulation), IRB/IEC-approved informed consent.

If applicable, in cases where the participant's representative(s) gives consent (if allowed according to local requirements), the participant must be informed about the study to the extent possible given his/her understanding. If the participant is capable of doing so, he/she must indicate agreement by personally signing and dating the written informed consent document.

Informed consent must be obtained before conducting any study-specific procedures (e.g. all of the procedures described in the protocol). The process of obtaining informed consent must be documented in the participant source documents.

Per [Section 4.6](#) during a Public Health Emergency as declared by local or regional authorities (i.e. pandemic, epidemic or natural disaster), that may challenge the ability to obtain a standard written informed consent due to limits that prevent an on-site visit, the investigator may conduct the informed consent discussion remotely (e.g. telephone, videoconference) if allowable by local health authorities.

Guidance issued by local regulatory bodies on this aspect prevail and must be implemented and appropriately documented (e.g. the presence of an impartial witness, sign/dating separate ICFs by trial participant and person obtaining informed consent, etc.).

Novartis will provide to investigators in a separate document a proposed informed consent form that complies with the ICH GCP guidelines and regulatory requirements and is considered appropriate for this study. Any changes to the proposed consent form suggested by the investigator must be agreed by Novartis before submission to the IRB/IEC.

Information about common side effects already known about the investigational drug can be found in the Investigator's Brochure (IB). This information will be included in the participant informed consent and should be discussed with the participant during the study as needed. Any new information regarding the safety profile of the investigational drug that is identified between IB updates will be communicated as appropriate, for example, via an investigator notification or an aggregate safety finding. New information might require an update to the informed consent and then must be discussed with the participant.

The following informed consents are included in this study:

- Main study consent, which also includes:

CCI

- A subsection that requires a separate signature for the “Optional Consent for Additional Research” to allow future research on data/samples collected during this study, and for the “Optional consent for activities that may be done outside of the study site”
- As applicable, Pregnancy Outcomes Reporting Consent for female participants who took study treatment

CCI

Women of childbearing potential must be informed that taking the study treatment may involve unknown risks to the fetus if pregnancy were to occur during the study and agree that in order to participate in the study they must adhere to the highly effective contraception requirements.

CCI

A copy of the approved version of all consent/assent forms must be provided to Novartis after IRB/IEC approval.

## 8 Visit schedule and assessments

The assessment schedule ([Table 8-1](#)) lists all of the assessments and study visits. All data obtained from these assessments must be supported in the participant's source documentation.

Participants should be seen for all visits/assessments as outlined in the assessment schedule ([Table 8-1](#)) or as close to the designated day/time as possible. If a visit has a specified visit window, all attempts to hold the visit within that specific window is necessary because the assessments are timing-critical for those visits. Missed or rescheduled visits should not lead to automatic discontinuation.

Participants who discontinue from study treatment are to return for the end of study visit as soon as possible and attend the follow-up visits as indicated in the assessment schedule.

Participants who discontinue from study or withdraw their consent/oppose the use of their data/biological samples should be scheduled for a final evaluation visit if they agree, as soon as possible, at which time all of the assessments listed for the final visit will be performed. At this final visit, all dispensed investigational product should be reconciled, and the adverse event and concomitant medications not previously reported must be recorded on the eCRF.

The "X" in the table denotes the assessments to be recorded in the clinical database or received electronically from a vendor. The "S" in the table denotes the assessments that are only in the participant's source documentation and do not need to be recorded in the clinical database.

As per [Section 4.6](#), during a Public Health Emergency as declared by local or regional authorities (i.e. pandemic, epidemic or natural disaster that limits or prevents on-site study visits), alternative methods to obtain needed assessments may be implemented by the investigator as the situation dictates. If allowable by a local health authority and depending on operational capabilities, phone calls, virtual contacts (e.g. tele consult) or visits by site staff/home nursing staff to the participant's home, can replace on-site study visits, for the duration of the disruption until it is safe for the participant to visit the site again.

The preferred sequence of data collection during study visits that do not include pharmacokinetic sampling is vital signs, spirometry, blood sampling (all labs and biomarkers), SPT, and then DBPCFC, as applicable per visit.

**Study drug must be administered prior to DBPCFC at end-of-treatment visits on Days 26 and 28.**

For visits that do include pharmacokinetic sampling (Days 8 and 25), every effort will be made to take the pharmacokinetic sample at the protocol specified time points. ECG in triplicate is required pre and post dose on these visits. The order of assessments on PK visit days is: ECG (in triplicate), pre-dose PK blood draw, dosing at 0h followed by ECG after dosing but before 0.5h PK blood draw timepoint.

Please ensure the order of assessments is respected consistently.

**Table 8-1 Assessment Schedule**

Period	Screening			Treatment									End of Treatment Assessment Visits								
Visit Name	Screening Visit 1	Screening Visit 2 (Part 1A DBPCFC) 	Screening Visit 3 (Part1B DBPCFC) 	Randomization (Start of Treatment)	Day 2 	Day 8 						Day 22	Day 25 						Day 26 (Part 2A DBPCFC) 	Day 28 (Part 2B DBPCFC) 	
Visit Numbers 	1	20	30	100	110	120						130	140						150	160	
Days	-30 to -15	-21 to -7	-10 to -3	1	2	8						22	25 -0 +2						26 -0 +2	28 -0 +2	
Time (post-dose)	-	-	-	-	-	0min	30min	1h	2h	3h	4h	-	0min	30min	1h	2h	3h	4h	-	-	
Clinic visit	X	X	X	X	X	X						X	X						X	X	
Medical history/current medical conditions	X																				
Demography	X																				
Concomitant Medications	X	X	X	X	X	X						X	X						X	X	
Informed consent	X																				
CCI																					
Inclusion / Exclusion criteria	X	X	X	X																	
Adverse Events	X	X	X	X	X	X						X	X						X	X	
Vital Signs	X	X	X	X		X						X	X						X	X	
Body Height	S																				
Body Weight	X	X	X	X		X							X						X	X	
Physical Examination	X	S	S	S		S						S	S						S	S	
Electrocardiogram (ECG) 	X					X	X						X	X							
Spirometry 	X	X	X																X	X	
Pregnancy and assessments of fertility 	S	S	S	S		S						S	S						S	S	

[illegible]

[illegible]

Period	Post-Treatment Follow-Up	
Visit Name	Day 31 End of Study 	Post Study Safety Tele-Visit
Visit Numbers 	1999	
Days	31 -0 +2	Last treatment +30 days ±5
Time (post-dose)	-	-
Clinic visit	X	
Medical history/current medical conditions		
Demography		
Informed consent		
CCI		
Inclusion / Exclusion criteria		
Adverse Events	X	X
Vital Signs	X	
Body Height		
Body Weight		
Physical Examination	S	
Electrocardiogram (ECG) 		
Spirometry 		
Pregnancy and assessments of fertility 	X	
Tuberculosis test		
Urinalysis	X	
Hematology	X	
Clinical Chemistry	X	
Coagulation Panel	X	
Hepatitis and HIV Screen		
Liver function test 	X	
Outpatient PK visits		
PK blood collection	See table below	

Period	Post-Treatment Follow-Up	
Visit Name	Day 31 End of Study 	Post Study Safety Tele-Visit
Visit Numbers 	1999	
Days	31 -0 +2	Last treatment +30 days ±5
Time (post-dose)	-	-
Total IgE; Peanut CCI IgE & IgG4; CCI	X	
Blood collection for specific immunoglobulin	X	
CCI		
Skin Prick test		
Double Blind Placebo Controlled Food Challenge (DBPCFC) 		
Unblinding of Allergen/Placebo for DBPCFC part 1B and part 2B 		
Study drug dispensation		
Study drug administration 		
Study drug accountability		
Providing rescue medication, counseling, training & accountability 		

x Assessment to be recorded in the clinical database or received electronically from a vendor

 Visit structure given for internal programming purpose only

 The DBPCFC has two parts: Parts A and B for both the screening DBPCFC and the End of Treatment DBPCFC will be done at least 2 days apart, but will not exceed 7 days apart, IRT will be called on day of Part1A and Part 2A to randomize participant to order of placebo/allergen dosing.

 Blood work at this visit is to be drawn prior to CCI dose. Participants should be instructed to hold their CCI dose until the end of the clinic visit.

 Triplicate ECGs will be conducted on days of PK blood draws. Triplicate ECGs should be performed at two timepoints: timepoint 0h before PK has been drawn but before dosing of study drug, and then again after dosing but before PK timepoint 0.5 h

 Only to be performed in participants diagnosed with asthma.

 Serum pregnancy test required at 1st screening visit for appropriate subjects and End of Study visit. Urine pregnancy test required at all other visits.

 Hepatitis B reactivation monitoring will be performed as needed: only in participants who are positive for HBcAb and negative for HBsAg and HBV-DNA at screening: HBsAg, HBV-DNA

 CCI

 CCI

 Unblinding with call to IRT occurs a minimum of 30 minutes after last dose of allergen/placebo administration. Determination of final exclusion criteria regarding reaction/no reaction to placebo can be met with this unblinding.

 Study drug will be dosed at home CCI by patient from Day 1 throughout the study. On days with clinic visits, study drug will NOT be taken at home in the CCI. The participant will take their CCI dose at the clinic at the specified time (based on assessment schedule for the visit).

 Assessment to be recorded in the source documentation only.

 End of treatment visit must be a minimum of 3 days after DBPCFC Part 2B. This visit may not be sooner than 72 hours from last study dose.

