## **6.2.4 Restriction for study participants**

### **6.2.4.1 Dietary restrictions and smoking**

Participants may take treatment with or without food, and choice should be recorded on paper patient diary each day. If taken without food, the study medication should be taken with a glass of water [240 milliliters (mL)] at least 2 hours after the last meal and 1 hour before the next meal. Participants must continue to avoid all food(s) to which they have allergies.

On PK assessment days (Day 8 and Day 25), all participants will fast for at least 10 hours (ideally overnight), including no light breakfast or snacks. Staff will inquire about approximate time patient took study treatment on the night prior to PK assessment days. This time will be recorded in eCRF. Participants will then take their study medication on site with water, but without food when instructed by site staff. Participants will continue to fast for at least 4 hours thereafter. No fluid intake other than that given at the time of dosing is allowed from 2 hours before until 2 hours after dosing, as indicated by FDA Bioequivalence Guidance for Industry (Revised Guidance for Industry on Bioavailability and Bioequivalence Studies for Orally Administered Drug Products-General Considerations; 68 FR 13316, [CDER 2003](#)). Participants should have a fluid intake of at least 240 mL every 4 hours during waking hours on PK assessment days in addition to fluid taken with meals and medication.

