#### 8.4.2 Electrocardiogram (ECG)

ECGs will be measured at Screening Visits 1, and on Days 8 and 25. Refer to [Table 8-1](#).

ECGs must be recorded after 10 minutes rest in the supine position to ensure a stable baseline/according to the ECG investigator manual. Refer to [Section 8](#) for order of assessments.

To provide additional cardiac safety data on remibrutinib, particularly regarding QT prolongation, ECGs will be performed in triplicate. At all visits where PK samples are collected (Days 8 and 25), pre and post-dose ECG assessments should be collected. Pre dose should be collected before the PK blood draw. Post dose assessment should be measured between the 0h and 0.5h PK sampling timepoints (i.e. after first PK sample and study drug dosing at 0h but before the second PK sample at 0.5h) and the mean QTcF value for each timepoint will be calculated from the triplicate ECGs for each participant.

Triplicate 12-lead ECGs are to be collected approximately 2 minutes apart for central analysis with ECG machines supplied by the core laboratory. Each ECG will be sent electronically for central review directly from the ECG machine. For all ECG tracings, a certified copy on non-heat-sensitive paper (e.g. appropriately signed and dated photocopy of the original ECG tracing) must be archived at the study site. The participant's number, the date, actual time of the tracing, and study code must appear on each page.

The mean QTcF value for each visit will be calculated from the triplicate ECGs for each participant. The Fridericia QT correction formula (QTcF) should be used for clinical decisions (e.g. at the screening visits to assess eligibility). The investigator must calculate QTcF if it is not auto calculated by the ECG machine.

Additional, unscheduled, safety ECGs may be repeated at the discretion of the investigator at any time during the study as clinically indicated. For any ECGs with participant safety concerns, two additional ECGs must be performed to confirm the safety finding. ECG safety monitoring, or a review process, should be in place for clinically significant ECG findings at screening before administration of study treatment and during the study.

Clinically significant abnormalities must be recorded on the eCRF as either medical history/current medical conditions or adverse events as appropriate.

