##### 8.5.2 Pharmacokinetics

PK samples will be collected at the visits and timepoints defined in the assessment schedule (Table 8-1).

PK assessment will be limited to 6 time points at each visit to characterize peak exposures of remibrutinib (0, 0.5, 1, 2, 3, 4 hours after intake of study medication, respectively). Samples should be taken as close to the given time (0, 0.5, 1, 2, 3, 4 hours post dose) as possible and the sampling time must be recorded. CCI

PK samples will be obtained and evaluated in all participants on active treatment. Follow instructions outlined in the laboratory manual regarding sample collection, numbering, processing and shipment.

All samples will be given a unique sample number as per lab manual. The actual sample collection date and time will be entered on the appropriate eCRF page.

CCI

If participants cannot visit the site for protocol specified PK assessments (per Section 4.6), an alternative collection method (e.g. home nursing) may be used if available. Samples should then be sent to site for processing and shipment as per a normal site visit.

Remibrutinib blood concentrations will be determined by a validated Liquid Chromatography-Mass Spectrometry (LC-MS/MS) method. Concentrations will be expressed in mass per volume units (ng/mL) and will refer to the free base. Concentrations below the LLOQ will be reported as “zero” and missing data will be labeled as such in the Bioanalytical Data Report.

The number of samples/blood draws collected will not exceed those stated in the protocol.

A non-validated method will be used for metabolite investigations as needed.

For standard PK abbreviations and definitions see the list provided at the beginning of this protocol. The following PK parameters will be determined from the blood concentration time data using the actual recorded sampling times and non-compartmental method(s) with Phoenix WinNonlin (Version 6.4 or higher): Cmax, Tmax, AUClast, AUCtau. Additional PK parameters may be determined as needed.

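### On PK Days 8 and 25, a footnote in Tables 8-1 and 8-2 holds the dose to the end of the visit, against the 0 h dosing that the PK samples and post-dose ECG require

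*Protocol*

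**What the plan says.** Footnote 3 of Protocol Table 8-1 and footnote 2 of Table 8-2 carry the same two instructions: blood work comes before the dose, and "Participants should be instructed to hold their CCI dose until the end of the clinic visit". In both tables the marker sits on Day 2, Day 8 and Day 25, with no exception for the days with PK sampling.

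The rest of the protocol places the dose early in the visit on Days 8 and 25:

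- Section 8 gives the order as triplicate ECG, then "pre-dose PK blood draw, dosing at 0h followed by ECG after dosing but before 0.5h PK blood draw timepoint". It then asks sites to keep to that order every time.
- Table 8-1 footnote 4 has a triplicate ECG before dosing, "and then again after dosing but before PK timepoint 0.5 h".
- Table 8-1 footnote 11 has the participant take the "dose at the clinic at the specified time (based on assessment schedule for the visit").
- Section 8.4.2: "Post dose assessment should be measured between the 0h and 0.5h PK sampling timepoints".
- Section 8.5.2: "PK assessment will be limited to 6 time points at each visit to characterize peak exposures of remibrutinib". The times listed are 0, 0.5, 1, 2, 3 and 4 h from intake.
- Section 6.2.4.1 has the drug taken on site, fasting, on PK days. It adds: "Participants will continue to fast for at least 4 hours thereafter".
- In both tables the time scale for Days 8 and 25 runs from 0 min to 4 h and is labelled as post-dose.

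**The concern.** A site that works from the schedule tables meets two incompatible orders for the same visit. If it follows the footnote, the samples labelled 0.5 to 4 h and the ECG labelled post-dose are all collected before the drug is given. The concentrations would then reflect what remains from the previous dose, not the absorption of the clinic dose.

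The PK parameters are a secondary endpoint (Protocol Table 2-1), and Section 4.2 intends the exposure data for the PK/PD assessment and paediatric dose selection. Section 8.4.2 gives QT prolongation as the particular reason for the triplicate ECGs. A pre-dose value filed under a post-dose label is worse than a missing one, because it enters the summaries unnoticed and understates peak exposure and any QT effect that follows dosing.

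**Working it through.** The plan gives no figure on this point, so the check compares texts and counts scheduled assessments.

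**1. Where the instructions overlap.** The hold applies to Days 2, 8 and 25. PK sampling takes place on Days 8 and 25 (Table 8-2; Section 8). Day 2 has no PK samples, so the hold is workable there. The conflict is confined to Days 8 and 25.

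**2. Whether both can be followed.** Section 8 puts the dose between the 0 h and 0.5 h samples, and the last sample comes 4 h after intake. A dose held to the end of the visit comes after the last sample. No reading of the visit satisfies both orders. Table 8-2 shows this most plainly: PK is the only blood collection it schedules, its footnote puts blood work before the dose, and five of its six times on these days are post-dose.

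**3. Which dose is held.** The label is redacted, so this is an inference.
- Section 6.1.3 and Table 8-1 footnote 11 describe a dose withheld at home on clinic days and taken at the visit.
- Section 6.2.4.1 records separately the time of the dose taken the night before a PK day.
- A hold to the end of the visit would have little purpose for a dose not due during the visit.
- Against this, Section 6.1.3 also has a redacted dose label for one that is not given on the day of the last challenge. The redaction therefore hides more than one label, and the clinic dose is the likely reading, not a proven one.

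**4. Consequence at one visit where the footnote is followed.**
- PK samples scheduled: 6. Samples meant to be post-dose: 5. Share turned pre-dose: 5/6 = 83%.
- Triplicate ECG sets scheduled: 2. Sets turned pre-dose: 1 of 2.
- If a participant's visits on both days went this way: 10 of 12 PK samples and 2 of 4 ECG sets.
- Cmax, Tmax and AUC for that visit would not describe the clinic dose. The PK loss matters only for participants on active drug at that visit.

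**5. Frequency.** The documents give nothing from which to estimate the share of visits affected. The range runs from none upwards.

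**The case against.** The strongest reply is that the protocol already settles the matter. The PK-day order is stated explicitly in Section 8, sites are asked to respect it, and several other sections repeat it. The footnote looks like a Day 2 instruction whose marker was extended too far. To do harm, a site would have to draw five timed samples on a post-dose scale without having given a dose, and most sites would query that first. There are also safeguards. Sampling times are recorded and used in the PK calculation (8.5.2), ECG tracings carry their actual time (8.4.2), and a dose taken too early on a PK day leads to rescheduling (6.1.3). Flagged concentrations, and participants with deviations that affect PK, stay out of the PK set (Protocol 12.1; SAP 2.2).

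Much of this stands and is why the point is minor. It does not remove the contradiction, which remains an operative instruction to sites. The safeguards are also partial: actual sampling times reveal a late dose only when compared with the dose time, the rescheduling rule covers early rather than late dosing, and SAP Table 2-1 lists no deviation code for PK dose timing.

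Three stronger readings are tempting, and the documents do not support them:

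- A reader might infer that PK and ECG data from all Day 8 and Day 25 visits are at risk, and count every scheduled sample. Such a total measures the schedule, not the damage. Nothing shows that any site followed the footnote.
- A reader might infer that the clock time of the clinic dose is not a required entry, since Section 6.1.3 only permits dosing information to be collected at PK visits. Part of Section 8.5.2 is redacted and the drug-administration row of Table 8-1 cannot be read, so no gap can be asserted. Sections 6.3.2 and 6.6 require dosing errors and missed or altered doses to be recorded.
- A reader might infer an effect on the primary endpoint, because Section 6.3.2 counts a dose more than 3 hours late as missed. Two held doses out of at least 28 (assuming at least one dose a day for 28 days) is 2/28 = 7%, below the 20% limit in Section 6.7.1. One on Day 25 cannot by itself make three consecutive days. Held doses alone would not bar anyone from the challenge.

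**Conclusion.** The inconsistency is real and sits in the current text of both tables. It is an internal inconsistency, not a disputed design choice, and its severity is minor. Where the footnote is followed, the loss at that visit is 5 of 6 PK samples and the post-dose triplicate ECG. The number of such visits is unknown and may be zero. The conclusion assumes that the redacted label means the clinic dose, which the surrounding text supports strongly but does not prove. The responder analysis, its significance level, power and sample size do not use these data and are unaffected.

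**What to change.** In both tables, do one of the following:

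- limit the end-of-visit hold to Day 2; or
- reword it for Days 8 and 25 so that the dose is held until after the pre-dose ECG and the 0 h PK sample and is then given at 0 h. The sentence on blood work before the dose should likewise refer only to pre-dose samples on those days.

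If visits remain, send sites a short clarification. Before database lock, compare recorded dose times with PK and ECG times for Days 8 and 25, and flag records where the dose came after nominally post-dose assessments.

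The cost is footnote wording in two tables, one site letter if still useful, and one data check. No visit or sample is added. For visits already completed, some dose times may have to be taken from source documents.
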